10.2.1 Visit 1: Screening from Day -42 to Day -1

The following activities will be performed:

- An explanation of the purpose, procedures, potential risks, and benefits of this study will be provided to the patient.

- Informed consent signature and date will be collected.
- If required locally, the locally provided consent for the required HIV screening test will be collected.
- Call IRT to assign patient number and register screening visit.
- Patient demography will be recorded.
- Medical/surgical/smoking/alcohol history.
- Review of prior and concomitant medication history.
- Family cardiovascular history.
- Full physical examination.
- GCA clinical assessments (including disease flare).
- Measure vital signs (including systolic and diastolic BP [mmHg], HR [beats per minute], body temperature [°C], and height [cm]).
- Body weight [kg].
- Perform blood sampling (fasting) for the following tests:
 - Hematology, chemistry.
 - Fasting lipids, fasting glucose and fasting insulin.
 - HbA1c.
 - CRP and ESR.
 - Virology.
 - Serum β -hCG pregnancy test (for WOCBP).
- Tuberculosis assessment including Quantiferon gold testing.
- Urinalysis (dipstick)
- 12-lead ECG.
- Perform chest X-ray if not performed at least 12 weeks prior to screening visit date.
- Confirmation of eligibility by the Investigator.
- Schedule a Visit 2 (D1, Week 0) within a maximum of 42 days from Visit 1.

Note: if the ultrasound is being used as a diagnostic tool for GCA to satisfy the Inclusion Criteria I01, the image needs to be submitted to the central reader for confirmation of eligibility.

10.2.2 Double blind period (52 weeks)

10.2.2.1 Visit 2/Baseline visit (Day 1, Week 0)

- Review of concomitant medication.
- Confirm eligibility by review of Inclusion/Exclusion Criteria.
If the patient meets all the inclusion criteria and does not meet any exclusion criteria, please conduct the following procedures in the recommended order, if possible:
- Call IRT to randomize the patient and obtain the initial treatment kit assignments.
- If the patient has been selected to complete the immunophenotyping blood sampling, the system will provide this information during the call.
- Administer PRO questionnaires (EQ-5D, FACIT-Fatigue, SF-36v2, HAQ-DI) and VAS.

Note: PRO questionnaires should be completed prior to any significant interaction with the study team and prior to any physical examination or sampling.

- Measure vital signs (including systolic and diastolic BP [mmHg], and HR [beats per minute], body temperature [°C]).
- Body weight (kg).
- GCA clinical assessments (including disease flare).
- Complete physician global assessment (MD-VAS).
- Inquire about AEs/SAEs.
- Tuberculosis assessment.
- Targeted physical examination (including head, eyes, ears, neck and throat, skin, respiratory, cardiovascular, neurologic, lymphatic examinations and abdominal examination).
- GTI Assessment.
- Bone density assessment by DXA (dual-energy x-ray absorptiometry) (± 2 week time window is allowed at baseline visit).

Note: Bone density assessment is not required if already available within 12 weeks prior to screening visit.

- Perform blood sampling (prior to administration of IMP) for the following tests:
 - Hematology and chemistry.
 - ANA.
 - CRP and ESR.
 - Serum sarilumab and ADA.
 - Biomarkers IL-6, sIL-6R.

- Serum and plasma sampling for circulating protein (for consented patients only).
- Sample for DNA and RNA for those patients who have consented to pharmacogenetics.
- Sample for circulating immune cell phenotyping for patients identified to perform this test.
- Perform urine pregnancy test (for WOCBP).
- Dispense patient diary to record injections performed at home (date, time, injection location, and local reaction or any medical events pertaining to the injection).
- IMP training. Provide instructions on preparation and self-injection of the prefilled syringes and the use of the weekly blister packs of prednisone. Document this training in the patients study file. Note: If the patient is unable or unwilling to perform the SC injections themselves, arrangements must be made for qualified site personnel and/or caregiver to administer SC study drug every 2 weeks for doses that are not scheduled to be given at the study site.
- Dispense and administer IMP. Patients will be monitored for at least 30 minutes or up to 2 hours as per country specific requirements after first dose of IMP for any signs or symptoms of a hypersensitivity reaction.
- Schedule an appointment for the next visit.

10.2.2.2 Visit 3 (Day 15 ±3, Week 2)

- Review of concomitant medication.
- Dispense new patient diary and review last visit patient diary.
- Measure vital signs (including systolic and diastolic BP [mmHg], HR [beats per minute], and body temperature [°C]).
- GCA clinical assessments (including disease flare).
- Inquire about AEs/SAEs.
- Tuberculosis assessment.
- Perform blood sampling (prior to administration of IMP) for the following tests:
 - CRP and ESR.
 - Serum sarilumab.
 - Biomarkers IL-6, sIL-6R.
 - Serum and plasma sampling for circulating protein (for consented patients only).
 - Sample for RNA for those patients who have consented to pharmacogenetics.
- Administration of IMP. Patients will be monitored for at least 30 minutes or up to 2 hours as per country specific requirements after first dose of IMP for any signs or symptoms of a hypersensitivity reaction.

- Call IRT to register visit and obtain next treatment kit assignments.
- Schedule an appointment for the next visit.

10.2.2.3 Visit 4-11 (Day 29 ±3, Week 4 to Day 281±3, Week 40)

- Administer PRO questionnaires (EQ-5D, FACIT-Fatigue, SF-36v2, HAQ-DI) (**Applicable only at Visits 6 and 9**; at these visits PRO questionnaires should be completed prior to any significant interaction with the study team and prior to any physical examination or sampling).
- Review of concomitant medication.
- Dispense new patient diary and review last visit patient diary.
- Measure vital signs (including systolic and diastolic BP [mmHg], HR [beats per minute], and body temperature [°C]). (**Applicable only at Visits 6, 9 and 11**).
- Measure body weight (Kg) (**Applicable only at Visits 6, 9 and 11**).
- GCA clinical assessments (including disease flare).
- Complete physician global assessment (MD-VAS) at Visits 6 and 9.
- Inquire about AEs/SAEs.
- Tuberculosis assessment.
- Targeted physical examination (including head, eyes, ears, neck and throat, skin, respiratory, cardiovascular, neurologic, lymphatic examinations and abdominal examination) (**Applicable only at Visits 6, 9, and 11**).
- GTI Assessment (**Applicable only at Visits 6, 9 and 11**).
- Perform blood sampling (prior to administration of IMP) for the following tests:
 - CRP and ESR.
- Perform blood sampling (fasting, prior to administration of IMP) for the following tests: (**Applicable only at Visits 4, 6, 9 and 11**)
 - Hematology and chemistry.
 - Fasting lipids, fasting glucose and fasting insulin.
 - HbA1c.
- Perform blood sampling (prior to administration of IMP) for the following tests: (**Applicable only at Visits 4, 6, 7 and 9**)
 - Serum sarilumab.
 - **Note:** Additional sample is to be drawn 4-7 days after **Visit 9** dosing. May be performed at the patient's home, if compatible with local organization.
 - Sample for circulating immune cell phenotyping for patients identified to perform this test. (**Applicable only at Visits 4 and 9**).

- Perform blood sampling (prior to administration of IMP) for the following tests: **(Applicable only at Visits 6 and 9)**
 - Antidrug antibody.
 - Biomarkers IL-6, sIL-6R.
 - Serum and plasma sampling for circulating protein (for consented patients only).
- Perform urine pregnancy test (for WOCBP).
- Call IRT to register visit and obtain next treatment kit assignments.
- Administration of IMP. Patients will be monitored for at least 30 minutes or up to 2 hours as per country specific requirements after first dose of IMP for any signs or symptoms of a hypersensitivity reaction.
 - Where the visit interval will exceed 4 weeks (**Applicable only at Visits 9, 10 and 11**), interim shipments of IMP to patients home may be performed using DTP shipping (according to local regulations and logistics), in order to provide the patient with only 4 weeks IMP at a time in order to minimize compliance errors.
- Schedule an appointment for the next planned visit.

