1.2 STUDY FLOW CHART

VISIT	V1	V2	V3	V4	V5	V6	V7	V8	V9	V10	V11	V12 (EOT)	V13	V14 (EOS)
DAY	D -42 to D -1	D1	D15 (±3)	D29 (±3)	D57 (±3)	D85 (±3)	D113 (±3)	D141 (±3)	D169 (±3)	D225 (±3)	D281 (±3)	D365 (±3)	D407 (±3)	D532 (±3)
WEEK		Wk 0	Wk 2	Wk 4	Wk 8	Wk 12	Wk 16	Wk 20	Wk 24	Wk 32	Wk 40	Wk 52	Wk 58	Wk 76
Eligibility														
Written informed consent	X													
Inclusion/exclusion criteria ^a	X ^a	X												
Patient demography	X													
Medical/surgical/smoking/alcohol history	X													
Prior medication history	X													
Family cardiovascular history	X													
Full physical examination	X											X		
Targeted physical examination ^b		X				X			X		X			
Confirm eligibility		X												
Randomization		X												
Call IRT	X	X	X	X	X	X	X	X	X	X	X	X		X
Treatment														
Initial treatment kit assignment (IRT)		X												
IMP administration ^c		X	X	X	X	X	X	X	X ^d	X ^d	X ^d	X		
Concomitant medication review	X	X	X	X	X	X	X	X	X	X	X	X	X	X
Dispense patient diary (for study medications)		X	X	X	X	X	X	X	X	X	X			
Compliance/review patient diary			X	X	X	X	X	X	X	X	X	X		

VISIT	V1	V2	V3	V4	V5	V6	V7	V8	V9	V10	V11	V12 (EOT)	V13	V14 (EOS)
DAY	D -42 to D -1	D1	D15 (±3)	D29 (±3)	D57 (±3)	D85 (±3)	D113 (±3)	D141 (±3)	D169 (±3)	D225 (±3)	D281 (±3)	D365 (±3)	D407 (±3)	D532 (±3)
WEEK		Wk 0	Wk 2	Wk 4	Wk 8	Wk 12	Wk 16	Wk 20	Wk 24	Wk 32	Wk 40	Wk 52	Wk 58	Wk 76
Vital signs														
Temperature, heart rate, blood pressure	X	X	X	X	X	X	X	X	X	X	X	X	X	X
Weight	X	X				X			X		X	X		
Height	X													
Efficacy														
GCA clinical assessments (including disease flare)	X	X	X	X	X	X	X	X	X	X	X	X	X	X
PROs ^e		X				X			X			X		
Physician Global Assessment (MD-VAS)		X				X			X			X		
GTI Assessment (excluding Bone Density assessment)		X				X			X		X	X		
Bone density assessment ^f		X										X		
Safety														
AE/SAE recording														
Tuberculosis assessment	X	X	X	X	X	X	X	X	X	X	X	X	X	
QuantiFERON®	X													
Chest X-ray ^g	X													
Laboratory testing														
Hematology ^h	X	X		X		X			X		X	X		
Chemistry ⁱ	X	X		X		X			X		X	X		
ANA		X										X		

VISIT	V1	V2	V3	V4	V5	V6	V7	V8	V9	V10	V11	V12 (EOT)	V13	V14 (EOS)
DAY	D -42 to D -1	D1	D15 (±3)	D29 (±3)	D57 (±3)	D85 (±3)	D113 (±3)	D141 (±3)	D169 (±3)	D225 (±3)	D281 (±3)	D365 (±3)	D407 (±3)	D532 (±3)
WEEK		Wk 0	Wk 2	Wk 4	Wk 8	Wk 12	Wk 16	Wk 20	Wk 24	Wk 32	Wk 40	Wk 52	Wk 58	Wk 76
Fasting lipids ^{j, k} /fasting glucose, fasting insulin ^l	X			X		X			X		X	X		

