9.2.2.4 Vital signs

Vital signs include temperature, BP, and heart rate (HR). They will be collected at every site visit prior to IMP administration. Weight will be collected at the screening Visit 1 (Day -42 to Day -1), Visit 2 (Week 0), Visit 6 (Week 12), Visit 9 (Week 24), Visit 11 (Week 40) and Visit 12 (Week 52). Weight should be taken with the patient wearing undergarments or very light clothing and no shoes and with an empty bladder. The same scale is recommended to be used throughout the study. Height will be collected at Visit 1 during screening only.

Body temperature

Body temperature must be collected using the same method for a given patient. Any fever (body temperature $\geq 38^{\circ}\text{C}$) associated with infection should be recorded as an AE and the Investigator should perform all investigations necessary to rule out infection.

Blood pressure

Blood pressure must be measured, using the same method consistently. Blood pressure is determined at each study visit using the same well-calibrated apparatus. The same arm should be used to measure BP throughout the study. The blood pressure should also be obtained with the patient in the same position (recumbent preferred) each time.

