1.3 DETERMINATION OF SAMPLE SIZE

The sample size calculations are based on the primary efficacy variable of sustained remission at Week 52. Data from another trial that evaluated the safety and efficacy of tocilizumab in a similar population show that the expected event rate in Group C (placebo with 26-week taper, n = 60) is 14% and in Group D (placebo with 52-week taper, n = 120) is 18% (1). Assuming a treatment difference of 40% and a significance level of 0.01 (2-sided) this will ensure that all comparisons of the primary endpoint in Group A (sarilumab 200 mg, n = 120) and Group B (sarilumab 150 mg, n = 60) compared to the 2 control groups will have at least 90% power. The sample size has also been selected to ensure adequate power for sensitivity analyses excluding acute phase reactants from the primary endpoint definition.

The above calculations were for the full enrollment. However, the number of randomized patients is 83 in 4 arms at the time of the premature termination of the study. In addition, based on patients' enrollment dates and the study discontinuation plan, only about 36 patients (out of 83) had an opportunity to complete the 52-week treatment period. For the cohort of patients who did not have an opportunity to complete the 52-week treatment period, it is not meaningful to define the endpoint of sustained remission at Week 52. Therefore, the analysis of primary endpoint will be limited to the cohort of patients who had an opportunity to complete the 52-week treatment period. Due to the small number of patients (n=36) in this cohort (see Section 2.3.1 for definition of the cohort), the powers on the primary endpoint are minimal. As a result, all the efficacy analyses will be descriptive in nature and all reported p-values will be nominal for the study.

Based on patients' enrollment dates, all enrolled patients (n=83) had an opportunity to complete at least 24 weeks of treatment, therefore, an additional endpoint, sustained remission at Week 24 is added in the SAP (see Section 2.1.3.1 for the detail definition). Table 1 provides the power calculations on the additional endpoint of sustained remission at Week 24. Due to the small number of patients in each individual treatment group, the power calculations were also provided for the comparison between the combined sarilumab groups (i.e., Group A+B) and the combined placebo groups (i.e., Group C+D) assuming the same effect sizes as mentioned above.

Table 1: Updated power calculations

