2.4.5.4 Analyses of vital sign variables

The summary statistics (including number, mean, median, SD, minimum, and maximum) of all vital signs variables (vital signs values and changes from baseline) will be calculated for each visit or study assessment (baseline, each post baseline time point, endpoint) by treatment group.

The incidence of PCSAs at any time during the TEAE period will be summarized by treatment group whatever the baseline level and/or according to the following baseline status categories:

- Normal/Missing
- Abnormal according to PCSA criterion or criteria

Listings will be provided with flags indicating the PCSA values.

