Appendix H Visit windows based on day ranges

Visit windows based on days relative to the first IMP dose will be used to map (see [Table 9](#)).

Table 9 - Day range for each scheduled visit in the DB period for efficacy, lab, vital sign, PK and ADA summaries

Visit Label	Target Day	Schedule A ^a	Schedule B ^b	Schedule C ^c	Schedule D ^d	Schedule E ^e	Schedule F ^f	Schedule G ^g	Schedule H ^h	Schedule I ⁱ	Schedule J ^j
Double-Blind Period											
Baseline	1	≤1	≤ 1	≤ 1	≤ 1	≤ 1		≤ 1	≤ 1	≤ 1	≤ 1
Week 2	15	>1'- 21							>1'-21	>1'-49	
Week 4	29	22-42				>1'-56	>1'-56	>1'-42	22 - 56		>1'-98
Week 8	57	43-70						43 - 70			
Week 12	85	71-98	>1'-126	>1'-126		57 - 126	57 - 126	71 - 98	57 - 98	50 - 126	
Week 16	113	99-126						99 - 126	99 - 140		
Week 20	141	127-154						127 - 154			
Week 24	169	155-196	127 - 224	127 - 266		127 - 224	127 - 224	155 - 196	141 - 266	127 - 266	≥ 99
Week 32	225	197-252						197 - 252			
Week 40	281	253-322	225 - 322			225 - 322	225 - 322	253 - 322			
Week 52	365	≥323	≥ 323	≥ 267	>1'	≥ 323	≥ 323	≥ 323	≥ 267	≥ 267	

a Includes temperature, heart rate, blood pressure, GCA clinical assessments (including disease flare), CRP, ESR

b Includes weight, glucocorticoid toxicity index (excluding bone density assessment)

c Includes physician global assessments (MD-VAS), patient reported outcomes and antibodies to sarilumab/ADA

d Includes bone density assessment, ANA

e Includes hematology: hemoglobin, hematocrit, red blood cell (RBC) count and morphology (if RBC count is abnormal), white blood cell (WBC) differential, platelet count, absolute neutrophil count (ANC) and chemistry: sodium, potassium, calcium, chloride, bicarbonate, total protein, creatinine and clearance, blood urea nitrogen (BUN), uric acid, lactate dehydrogenase (LDH), phosphate, albumin, ALT (SGPT), AST (SGOT), alkaline phosphatase (ALP), total bilirubin, conjugated bilirubin, and unconjugated bilirubin

f Includes HbA1c, fasting glucose, fasting lipids: triglycerides (TG), total cholesterol, HDL, LDL

g Includes urine pregnancy test

h Includes serum sarilumab

i Includes biomarkers-IL-6 and sIL-6R

j Includes immune cell phenotyping (whole blood)

* Includes value measured on day 1 but after the first IMP dose

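### The visit-by-visit instructions drop blood pressure, heart rate and temperature at five treatment visits where the flow chart, Section 9.2.2.4 and the SAP require them

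*Protocol*

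**What the plan says.** Protocol Section 10.2.2.3 lists the procedures for Visits 4 to 11 (Weeks 4 to 40). Its vital-signs bullet ends: "HR [beats per minute], and body temperature [°C]). (Applicable only at Visits 6, 9 and 11". The next bullet, body weight, carries the same three-visit qualifier.

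Elsewhere the documents say something different about vital signs:

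- **Protocol Section 9.2.2.4**, which defines them: "They will be collected at every site visit prior to IMP administration". It repeats the rule for one of them: "Blood pressure is determined at each study visit using the same well-calibrated apparatus".
- **Protocol Section 1.2 flow chart**: the row "Temperature, heart rate, blood pressure" is marked in all 14 visit columns. SAP Appendix A reproduces it unchanged.
- **SAP Appendix H, Table 9**: Schedule A, with a window at every on-treatment visit, "Includes temperature, heart rate, blood pressure, GCA clinical assessments (including disease flare), CRP, ESR".
- **SAP Section 2.4.5.4**: "The summary statistics (including number, mean, median, SD, minimum, and maximum) of all vital signs variables" are to be produced for each visit by treatment group.

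Only weight has a restricted schedule elsewhere. After screening, Section 9.2.2.4 collects it at "Visit 2 (Week 0), Visit 6 (Week 12), Visit 9 (Week 24), Visit 11 (Week 40) and Visit 12 (Week 52", and the flow chart agrees.

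**The concern.** The qualifier in 10.2.2.3 is an explicit instruction not to take the measurement at the visits it leaves out. Coordinators usually work from the visit-by-visit list, and nothing in that list signals an error. The omission also does not look intended. Every other visit section (Visits 1, 2, 3, 12, 13 and 14) asks for vital signs without restriction. Read literally, the protocol would measure them at Weeks 58 and 76, when patients are off drug, but skip them at five treatment visits.

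What is at stake is safety surveillance. Section 4.1 names serious infection as an important identified risk, and Section 9.2.2.4 makes a temperature of 38°C or more associated with infection a reportable event. At the five visits no targeted physical examination is scheduled, and at four of them (Visits 5, 7, 8 and 10) no hematology either. CRP is blinded to both assessors. A temperature reading there has value, as has blood pressure at Weeks 4 and 8, early in the prednisone taper. The by-visit summaries and the incidence of potentially clinically significant vital-sign values would rest on fewer readings from any such site.

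**Working it through.** There is no power or alpha figure to reproduce; this is a comparison of schedules.

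**Visits omitted.** Section 10.2.2.3 covers {4, 5, 6, 7, 8, 9, 10, 11}, which is 8 visits. Removing {6, 9, 11} leaves {4, 5, 7, 8, 10}, so 8 − 3 = 5 visits without vital signs: Weeks 4, 8, 16, 20 and 32. There are 10 post-baseline on-treatment visits (Weeks 2, 4, 8, 12, 16, 20, 24, 32, 40, 52), so 5 of 10 are lost.

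**Intervals between scheduled on-treatment readings.**

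| | Flow chart | Section 10.2.2.3 read literally |
|---|---|---|
| Weeks measured | 0, 2, 4, 8, 12, 16, 20, 24, 32, 40, 52 | 0, 2, 12, 24, 40, 52 |
| Gaps (weeks) | 2, 2, 4, 4, 4, 4, 4, 8, 8, 12 | 2, 10, 12, 16, 12 |
| Median gap | 4 | 12 |
| Longest gap | 12 | 16 |
| Post-baseline readings before Week 12 | 3 (Weeks 2, 4, 8) | 1 (Week 2) |

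**Volume through Week 24.** SAP Section 1.3 says "all enrolled patients (n=83) had an opportunity to complete at least 24 weeks of treatment". The scheduled post-baseline visits to that point are Weeks 2, 4, 8, 12, 16, 20 and 24, which is 7. Weeks 4, 8, 16 and 20 are the omitted ones, which is 4. With full attendance:

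- scheduled sets: 83 × 7 = 581
- omitted if every site followed 10.2.2.3: 83 × 4 = 332
- omitted if every site followed the flow chart: 0

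The range is therefore 0 to 332 of 581, and the documents do not say where in it the trial falls.

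**What is untouched.** The toxicity index is scored at Weeks 12, 24, 40 and 52, all of which keep their blood-pressure reading. Remission, flare, CRP and taper adherence do not use the vital-sign measurements. The other Schedule A items (GCA assessment, CRP, ESR) carry no such restriction in 10.2.2.3.

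**Source of the restriction.** Within Visits 4 to 11, Section 9.2.2.4 and the flow chart place weight at Visits 6, 9 and 11 only, exactly the list on the vital-signs bullet above it. Carry-over between adjacent bullets is a reasonable inference, not something the documents state.

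**The case against.** The best reply is that the rest of the protocol settles the matter. The assessment-schedule part of the Clinical Trial Summary tells patients and investigators to respect the visit schedule in the flow chart. Section 9.2.2.4, both flow charts and SAP Table 9 all agree against one parenthesis. This makes omission less likely. It is not a precedence rule, though: the sentence after it deals with changed visit dates, and the contrary instruction stays in the procedures.

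The safety consequence can also be pressed too far. Section 10.7.1 requires any infection to be reported as an adverse event, whatever the temperature. Fever is among the signs that the Efficacy Assessor reviews at each visit, and a clinical examination and history for tuberculosis are required at each visit. Adverse-event inquiry and ESR, which the Safety Assessor can see, continue. Unscheduled readings are allowed, and SAP Section 2.5.5 uses them. All of this stands. What would be lost is a scheduled measurement, so a fever or blood-pressure change could be noticed later; the duty to report would remain.

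The 332 figure needs every site to ignore the flow chart and every patient to attend. SAP Section 2.5.6 records on-site visit limits and remote assessments during the pandemic, so full attendance is doubtful. It is a ceiling and should be read as one.

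Finally, the SAP describes a terminated trial, with treatment to end by October 13, 2020 and follow-up by November 24, 2020. Correcting the text after those dates cannot recover readings.

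**Conclusion.** The point holds. The current text of Section 10.2.2.3 contradicts the flow chart, Section 9.2.2.4 and the SAP on when blood pressure, heart rate and temperature are taken. Followed literally, it removes 5 of the 8 visits it covers. The visit count and the intervals follow directly from the documents. The number of readings actually lost depends on which text each site used and on attendance, neither of which is given.

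The consequence is confined to safety monitoring and descriptive safety tables; no inferential result depends on these readings. This is an internal inconsistency that should be corrected because it is an operational instruction that is wrong as written, though it does not threaten the trial's conclusions.

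**What to change.** Delete the three-visit qualifier from the vital-signs bullet in Section 10.2.2.3, leave it on the body-weight bullet, and send sites a short clarification. All 8 visits then carry vital signs, in line with the flow chart, Section 9.2.2.4 and Schedule A. The measurements fall at visits already scheduled, so no visit, equipment or analysis is added.

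The SAP needs no change. Section 2.4.5.4 already reports the number of patients at each visit, and Section 2.4.5 already uses patients assessed as the denominator for potentially clinically significant abnormalities. Since the SAP was written for a trial that was closing, the useful step at reporting is to check whether missing vital signs cluster at Weeks 4, 8, 16, 20 and 32, and to say so if they do.
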